9.7.4. Potential Covariates and Confounders

In accordance with the FDA and Agency for Healthcare Research and Quality (AHRQ) guidance,^{45,70} the following variables may be considered potential covariates and confounders, as appropriate:

- Geographic region
- Maternal age at conception
- Calendar year at conception
- Maternal race
- Maternal ethnicity
- Proxies for maternal socioeconomic status, including maternal education, employment status, and income
- Maternal pre-pregnancy BMI, calculated from pre-pregnancy weight and height
- Gestational age at registry enrollment
- Method of conception
- Number of fetuses
- Concurrent maternal medical conditions, including thyroid abnormalities, infectious diseases (including coronavirus disease 2019 [COVID-19]), asthma, diabetes, hypertension, seizure disorder, autoimmune diseases, depression and other psychiatric disorders, hepatitis, sexually transmitted diseases, and uterine or cervical abnormalities (e.g., congenital uterine abnormalities)
- Concurrent pregnancy-related maternal medical conditions or pregnancy complications, including pregnancy-induced hypertension, pre-eclampsia, eclampsia, gestational diabetes, preterm labor, placenta previa, placental abruption, incompetent cervix, ectopic pregnancy, molar pregnancy
- Number of previous pregnancies
- Previous pregnancy outcomes (SAB, stillbirth, induced abortion, live birth)
- Previous pregnancy complications
- Characteristics of previous live births (preterm, SGA, LGA)
- Previous fetus/infant with congenital malformations (major and minor)
- Family history of congenital malformations (major and minor)
- Disease characteristics, including duration, BMI, and weight-related comorbid conditions
- Maternal exposure to other drugs or biological products, including prescription and non-prescription drugs, dietary supplements (including folic acid and prenatal vitamins), and vaccines (including COVID-19), during pregnancy and gestational age at exposure
- Maternal exposure to tobacco, alcohol, marijuana, and recreational or illicit drugs during pregnancy and timing of exposure
- Maternal weight change prior to pregnancy
- Maternal weight change during pregnancy
- Labor type (induced vs. spontaneous)
- Delivery method and complications

Some variables may not be captured due to country-specific privacy regulations. Data collected at each study site will abide by regulatory guidelines, local privacy laws, and national provisions (e.g., date of birth and race/ethnicity will not be collected from participants in Germany). The collection of race and ethnicity data in the US will comply to the FDA guidance for industry, Collection of Race and Ethnicity Data in Clinical Trials and Clinical Studies for FDA-Regulated Medical Products.⁴⁷

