7.4.3. Current Standard of Care

Although lifestyle modifications continue to be the first-line treatment for obesity, most people with obesity struggle to achieve and maintain weight loss with diet and exercise alone.³⁴⁻³⁹

Surgical treatments offer an effective alternative for some people with severe obesity, but bariatric surgery carries a risk in connection with the procedure and is not without post-surgical complications. Pharmacotherapy may therefore serve as a valuable adjunct to lifestyle intervention for individuals with obesity to achieve and sustain clinically relevant weight loss, improve comorbid conditions, and facilitate a healthier lifestyle.^{34,36,39}

As of 25 January 2025, a limited number of pharmacological options, including therapies with GLP-1 RA activity: semaglutide, tirzepatide, liraglutide; and non-GLP-1 RAs: orlistat, naltrexone-bupropion, setmelanotide, phentermine, phentermine-topiramate are approved for weight management in the US and the European Union (EU). All of these have shown effective weight loss, but generally only in the range of around 5% to 10% except for semaglutide and tirzepatide. The STEP 1 (NN9536-4373) trial data showed that treatment with semaglutide 2.4 mg resulted in a weight loss of up to 14.9% compared with 2.4% in the placebo group (treatment policy estimand).⁴⁰ SURMOUNT-1 (NCT04184622) data demonstrated that treatment with tirzepatide resulted in a higher weight loss of 20.9% at week 72 with 15 mg weekly doses compared with 3.1% in the placebo group (treatment regimen estimand).⁵

Additionally, since semaglutide and tirzepatide are administered once weekly, they offer a more convenient treatment option than existing weight management drugs and may improve treatment adherence.^{5,6} During pregnancy, lifestyle modifications are the primary tool for weight management.⁴¹⁻⁴³ Weight loss during pregnancy is generally discouraged and use of surgical and pharmacologic interventions are not recommended during, or immediately preceding, pregnancy due to known or suspected safety concerns as well as lack of data on safety of use during pregnancy.⁴⁴

Currently patients are advised to discontinue tirzepatide when pregnancy is recognized. However, it is expected that exposure during pregnancy may occur among real-world patients being treated for chronic weight management.

8. Research Question and Objectives

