- For induced abortion, reason (e.g., finding on prenatal test, risk to mother's health, undesired pregnancy)

Infant Outcome Information

Collected from pediatric HCP at 4 and 12 months post-delivery

- Infant weight, length, and head circumference at birth (if not provided at pregnancy outcome) and at 4 and 12 months of age
- Achievement of the developmental milestones in each Centers for Disease Control and Prevention (CDC)-defined category (social/emotional, language/communication, cognitive, and movement/physical development) at 4 and 12 months of age
- Congenital malformations (major and minor) and assessment of potential contributing factors
- Infant death, including date and cause of death
- Infant illnesses (e.g., neonatal hypoglycemia), infections, and hospitalizations
- Breastfeeding information, including breastfeeding start/stop dates, maternal medicinal and recreational exposures during breastfeeding, and low milk supply

Targeted Follow-up Information

Collected from HCP(s) – obstetric and/or pediatric – at any time after pregnancy outcome

- Details of congenital malformations (major or minor) or other conditions
- Etiology
- Exposures that may have had an impact on the outcome
- Additional factors that may have had an impact on the outcome
- Specific questions requested by the sponsor and/or the birth defect evaluator

Data collection may be restricted in some cases due to country-specific privacy/data protection regulations.

Data Reconciliation

Although data may be collected from multiple reporters, a hierarchy will be applied during analysis that prioritizes the response from the reporter that is most likely to have the most accurate information on a per variable basis. For example, for disease characteristics and medicinal exposures, the primary position would go to information reported by the prescribing HCP, followed by the obstetric HCP, pediatric HCP, and the patient. Pregnancy information would have the obstetric HCP as the primary reporter, followed by the prescribing HCP, pediatric HCP, etc. Infant-related variables will have pediatric HCP as primary, followed by obstetric HCP, and prescribing HCP. Generally, HCP-reported information will always be used for all reporting, with two exceptions: patient-reported exposures may be used for initial cohort classification while HCP verification is pending and patient-reported LMP may be used for pregnancy dating if both the HCP-reported LMP and EDD are missing.

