9.9. Study Size

9.9.1. Sample Size

Table 9.4 presents by outcome the sample size (number of live births or pregnant individuals, depending on the outcome) required in each cohort to detect a range of relative risks, from 1.5 to 5.5. Sample size calculations were performed with SAS® statistical software (version 9.4 or higher, SAS Institute, Cary, NC) for the outcomes using the Fisher's exact conditional test with Walters normal approximation method, and assuming a power of 80%, a 2-sided α level of 0.05, an equal number of individuals in each cohort (although other sampling ratios were considered), and observed prevalence of the outcomes in the comparator cohort equivalent to reference rates in the general population. These general population rates were obtained for most (but not all) of the outcomes from various sources, including the Metropolitan Atlanta Congenital Defects Program (MACDP), the National Vital Statistics System (NVSS), and published literature.

Although the registry aims to examine a variety of maternal, fetal, and infant outcomes, the target sample size for the registry is based on the primary outcome, overall prevalence of MCM, which also is the outcome with the most restrictive denominators and one of the lowest prevalence in the general population.

As shown in Table 9.4, 265 live births in the analysis population of each cohort are needed to detect a 3-fold increase in the overall prevalence of MCM between cohorts, or a relative risk of 3.

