To estimate the number of pregnant individuals who will need to be enrolled to result in 265 live births per cohort, several factors were considered, including the expected registry live birth rate, the proportion of enrolled individuals expected to be exposed to tirzepatide in the first trimester, and the proportion of enrolled individuals expected to be excluded from the analysis population. It was assumed that 90% of enrolled individuals would be exposed in the first trimester, 90% of enrolled pregnancies would result in a live birth,^{72,73} and 10% of enrolled individuals would be excluded from the analysis population due to the occurrence of pregnancy outcome prior to enrollment (retrospectively enrolled participants), exposure to a known teratogen or an investigational medication or congenital infectious agents during pregnancy (teratogen/investigational medication/congenital infectious agent-exposed participants), lack of pregnancy outcome data (participants lost to follow-up; assumed to constitute 5%), or inclusion of a prior pregnancy in the analysis population (subsequent pregnancies). These assumptions are based on experience with other similar study designs. To ensure adequate sample size in the main analysis population is achieved, enrollment of the main analysis population will be assessed throughout data collection. If higher than anticipated percentages of participants would be excluded from the analysis population, it will be assessed what (if any) potential mitigations should be implemented. It is also acknowledged that there could be some effective sample size loss due to the use of stabilized IPTW. The extent and potential mitigations for this will be assessed after approximately 100 participants have enrolled in each of the cohorts.

Given these assumptions, to attain 265 live births per cohort, 364 (=265/0.9/0.9/0.9) pregnant individuals would need to be enrolled in each of the three cohorts of the study population, and a

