Postnatal growth deficiency	10.0%	By definition	Live births	721	215	110	70	49	37	29	24	20
Infant developmental delay	13%	Rosenberg 2008 ⁸¹	Live births	532	158	80	50	35	26	21	17	14
Exploratory Objectives												
Heart Failure	0.12%	Mogos 2018 ⁸²	Pregnant individuals	667975	20706	10798	6952	5002	3853	3107	2588	2210

Outcomes ^a	Reference Prevalence in Unexposed Group	Reference	Denominator of Reference	RR= 1.5	RR= 2.0	RR= 2.5	RR= 3.0	RR= 3.5	RR= 4.0	RR= 4.5	RR= 5.0	RR= 5.5
Peripartum Cardiomyopathy	0.03%	Harper 2012 ⁸³	Live births	272189	82925	43251	27847	20039	15437	12450	10374	8858
Hyperemesis gravidarum	2.5% (0.3 to 3.5%)	ACOG 2015 ⁸⁴	Pregnant individuals	3171	962	500	321	230	176	142	118	100
Inadequate GWG	15% (12 to 25%)	CDC 2015 ⁸⁵	Pregnant individuals	448	132	67	42	29	22	17	13	11
LGA	10.0%	Hocquette 2021 ⁸⁶	Live births	721	215	110	70	49	37	29	24	20
Rapid infant weight gain	8% (5 to 14%)	Eckhardt 2016 ⁸⁷	Live births	925	278	143	91	64	49	39	32	27

Abbreviations: GWG = gestational weight gain; MCM = major congenital malformation; NA = not available; reference prevalence = prevalence of outcome in general population for pregnant individuals of any age; RR = relative risk; SAB = spontaneous abortion; SGA = small for gestational age.

^a Only outcomes with published reference rates in the general population are included in the table.

^b For induced abortion, an RR of 5.5 with a reference rate of 18.6% in the unexposed cohort would result in a rate above 100% in the exposed cohort.

^c Sampling ratio is 1:1 (Exposed: Tirzepatide Unexposed). Comparisons between tirzepatide exposed vs. AOM active comparator and tirzepatide exposed vs. AOM unexposed comparator will be conducted separately.

Notes: Sample size calculations were performed in SAS (version 9.4) for the outcomes using Fisher's exact conditional test with Walters normal approximation method, and assuming a power of 80% and a 2-sided α level of 0.05.

Table 9.5. Power to Detect a 3-fold Increase, by Study Outcome

Outcomes	Power Estimate
MCM	80%
Pregnancy-induced hypertension	>80%
Pre-eclampsia	>80%
Eclampsia	5.9%
Gestational diabetes	>80%
Heart failure	0%
Peripartum Cardiomyopathy	0%
Hyperemesis gravidarum	71.5%
Inadequate maternal weight gain	>80%
SAB	>80%
Stillbirth	21.4%
Induced abortion	>80%
Preterm birth	>80%
SGA	>80%
LGA	>80%
Postnatal growth deficiency	>80%
Rapid infant weight gain	>80%
Infant developmental delay	>80%

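### Pregnancy intention is not collected at enrollment although exposure plausibly depends on it, so weighting cannot fully remove this confounding, chiefly for induced abortion against the unexposed cohort

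*Protocol*

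**What the plan says.** Section 9.7.4 of the protocol introduces its covariate list by saying that "the following variables may be considered potential covariates and confounders, as appropriate". The list covers, among others, age, socioeconomic proxies, BMI, gestational age at enrollment, method of conception, previous pregnancy outcomes, supplements including folic acid, and tobacco, alcohol and drug use with timing. Section 9.8 adds history of fertility treatment. Pregnancy planning, intention and contraceptive use appear in neither section.

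The nearest item is in the pregnancy outcome data of Section 9.8: "For induced abortion, reason (e.g., finding on prenatal test", followed by risk to the mother's health and undesired pregnancy as further examples.

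On the link between exposure and planning, Section 7.4.3 says that drug treatment for weight is not recommended during pregnancy or just before it, and that "Currently patients are advised to discontinue tirzepatide when pregnancy is recognized". Section 9.6.3.1 directs recruitment for the comparator cohort toward former tirzepatide users whose last use was more than 25 days before conception.

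Induced abortion is a secondary outcome (Sections 8.2 and 9.3). Section 9.11.2.2 gives it an IPTW-adjusted relative risk in each of the two comparisons. The weights balance observable covariates only.

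**The concern.** A woman who plans a pregnancy and follows the advice in Section 7.4.3 stops the drug beforehand. If she stops more than 25 days before conception she is not exposed, and the recruitment plan may then seek her out as a comparator. A woman who conceives without planning is more likely to be exposed. Exposure is therefore plausibly enriched for unplanned pregnancies, and the unexposed cohort has no matching selection.

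Intention is also an obvious determinant of induced abortion. A common cause of exposure and outcome that is not recorded cannot enter the propensity model. The SAP may choose among the collected variables, but it cannot supply one that was never collected. The reason recorded after an abortion does not help, because it exists only for pregnancies that already have the outcome.

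At stake is a relative risk for induced abortion that could suggest a drug effect where there is none, or misstate the size of a real one.

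**Working it through.** **1. The protocol's own figures.** Section 9.9.1 works "using the Fisher's exact conditional test with Walters normal approximation method", "assuming a power of 80%, a 2-sided α level of 0.05, an equal number of individuals in each cohort". With n per cohort and comparator and exposed rates p0 and p1, the approximation is

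power = Φ( √(2n) · [asin√(p1 − 1/(2n)) − asin√(p0 + 1/(2n))] − 1.96 ).

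- Malformations, 3% vs 9%, n = 265: √530 × (0.3014 − 0.1795) − 1.96 ≈ 0.845, so power is about 0.80. This agrees with "265 live births in the analysis population of each cohort are needed to detect a 3-fold increase in the overall prevalence of MCM between cohorts".
- Induced abortion, reference 18.6%: the same formula returns 343, 100, 50 and 31 for relative risks of 1.5, 2.0, 2.5 and 3.0, as in Table 9.4.
- Enrollment: 265/0.9³ = 363.5, rounded up to 364.

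No sample-size figure is wrong. The formula is reused in step 4.

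**2. Bias factor for induced abortion.** Let u1 and u0 be the unplanned shares in the exposed and comparator cohorts, and k the relative risk of the outcome for unplanned vs planned. With no drug effect, the expected relative risk is

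B = [1 + u1(k − 1)] / [1 + u0(k − 1)].

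The protocol gives none of these inputs. All values below are assumptions.

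| u1 vs u0 | k = 3 | k = 5 | k = 10 |
|---|---|---|---|
| 60% vs 50% | 1.10 | 1.13 | 1.16 |
| 60% vs 40% | 1.22 | 1.31 | 1.39 |
| 80% vs 40% | 1.44 | 1.62 | 1.78 |
| 90% vs 40% | 1.56 | 1.77 | 1.98 |
| 90% vs 80% | 1.08 | 1.10 | 1.11 |

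Example: 80% vs 40% with k = 5 gives (1 + 0.8×4)/(1 + 0.4×4) = 4.2/2.6 = 1.62. Equal shares give 1.00 for any k. The last row is the kind of pattern to expect in Comparison #1, where both cohorts took a drug around conception.

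**3. Malformations and other weakly related outcomes.** With k = 1.2 and 60% vs 50%, B = 1.12/1.10 = 1.02. With k = 1.5 and 80% vs 40%, B = 1.40/1.20 = 1.17.

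**4. Would such a bias show as significant?** For induced abortion the denominator is the analysis population. The protocol assumes 10% exclusions, so 364 × 0.9 ≈ 328 per cohort. At an 18.6% comparator rate, a purely spurious relative risk of 1.5 (27.9%) gives √656 × (0.5548 − 0.4479) − 1.96 ≈ 0.78, so the probability of p < 0.05 is about 0.78. For a spurious 1.25 it is 0.28. If the comparator rate were 5% (assumed), these fall to 0.21 and 0.08. A lower rate than 18.6% is plausible: Table 9.4 states that reference per live births, whereas Table 9.7 divides by individuals, and Section 9.13 notes that abortions before enrollment are missed. The calculation ignores any loss of effective sample size from weighting.

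**The case against.** Much of the path from intention to outcome is measured: folic acid and prenatal vitamins, substance use with timing, gestational age at enrollment, method of conception, fertility treatment, previous induced abortion and socioeconomic proxies. A reader might infer from the missing item that weighting leaves this confounding untouched. The documents do not support that. The proxies remove part of it, and for malformations they cover the most obvious routes. They do less for induced abortion, where the decision itself turns on intention.

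Section 9.11.2.7 plans a quantitative bias analysis, and Section 9.13 concedes residual confounding. Both count in the protocol's favor. Neither names intention, though, and a bias analysis shows how strong a confounder would have to be; it does not adjust for one that could have been asked about.

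The advice in Section 7.4.3 applies to weight-loss drugs generally, so Comparison #1 is partly protected by design. The 25-day window counts some planners as exposed, and late, voluntary enrollment may narrow the difference further. These points stand and limit the concern largely to Comparison #2.

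Finally, p-values for secondary outcomes are nominal (Section 9.11.2), and the recorded reason for abortion helps interpret the result descriptively. That lowers the stakes without removing the bias from the estimate.

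**Conclusion.** The omission is real and cannot be repaired in the SAP. It matters mainly for the induced-abortion relative risk in Comparison #2, where plausible assumed inputs give a bias factor of about 1.1 to 1.8. More extreme inputs go higher, and similar cohorts bring it close to 1. It is probably smaller in Comparison #1. For malformations it is about 1.02 to 1.17 under the assumptions shown, against a design built to detect a relative risk of 3, so the primary analysis is not seriously threatened.

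A reader might go further and conclude that exposed pregnancies are largely unplanned, or that the adjusted abortion estimate would mainly reflect intention. The protocol's reasoning supports a dependence of exposure on planning, but it gives no figure for its strength, and the low end of the range is only 1.10. Neither conclusion is shown.

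**What to change.** - Add one item (planned / unplanned / unsure) to the Registration Form for Participants, asked at enrollment in all three cohorts. For prospectively enrolled participants this is before the pregnancy outcome.
- Add pregnancy intention to Section 9.7.4.
- List it in Section 9.8 as a participant-reported variable usable without provider confirmation. The data reconciliation rule there otherwise generally restricts analysis to provider-reported data, with two named exceptions.
- Include it in the propensity model for induced abortion. For other outcomes, check its balance and add it under the existing rule in Section 9.11.2.4 if it is imbalanced. Forcing it into every model could widen the weights for little gain.
- Name intention as a target of the quantitative bias analysis in Section 9.11.2.7 for induced abortion.

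The cost is one form question, short text changes and possibly a separate set of weights for induced abortion. The answer is self-reported after conception. It may be given reluctantly, given the US legal concerns noted in Section 9.13, and may be colored by prenatal test results, since the main analysis admits women enrolled after testing. It will be missing for anyone enrolled before the change. Enrollment may run to 31 December 2033 (Section 9.6.4), so an early change loses least.

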9.7.5. Other Variable Definitions and Ascertainment

Per the American College of Obstetricians and Gynecologists (ACOG), gestational age and the EDD should be determined by the obstetric HCP as soon as data are obtained regarding the last menstrual period (LMP), first accurate ultrasound, or both. The ACOG considers ultrasound measurement of the embryo or fetus in the first trimester (up to and including 13^{6/7} gestational weeks) the most accurate method to establish or confirm gestational age and discourages against changing the EDD based on subsequent ultrasounds. Any pregnancy without an ultrasound before 22^{0/7} gestational weeks to confirm or revise the EDD should be considered suboptimally dated. If the pregnancy resulted from assisted reproductive technology (ART), the obstetric HCP should use ART-derived gestational age (e.g., based on age of embryo and date of transfer) to determine EDD. The ACOG further recommends that the best estimate of EDD by the obstetric HCP, rather than estimates based on LMP alone, be used for research purposes.⁷¹

Based on ACOG's recommendations, the registry will collect the EDD from the obstetric HCP, and the HCP will report whether the EDD was calculated based on LMP, ultrasound, or ART data. If ultrasound-based, whether the ultrasound was performed before 14^{0/7}, before 22^{0/7}, or at 22^{0/7} gestational weeks or later will also be recorded. EDD data will be collected on each data collection form throughout pregnancy. If the HCP reports a corrected EDD on subsequent forms that is different from the EDD initially reported, the registry will evaluate whether a correction is appropriate, based on the timing of the correction and the methods used to determine the corrected EDD, and follow-up with the HCP, if needed.

The registry will conform to the ACOG recommendations for determining the 'best' EDD, and EDD will be used to calculate gestational age. Based on the EDD, the following will be calculated:

- First day of LMP, defined as 0^{0/7} gestational week, will be calculated as EDD minus 280 days (40 weeks)

Gestational age will be calculated as the number of weeks elapsed since the first day of LMP:

- Gestational weeks 0^{0/7} to 13^{6/7} will be considered the first trimester
- Gestational weeks 14^{0/7} to 27^{6/7} will be considered the second trimester
- Gestational weeks 28^{0/7} to pregnancy outcome will be considered the third trimester

DOC, defined as 2^{0/7} gestational weeks, will be calculated as first day of LMP plus 14 days (2 weeks).

If EDD is not reported by the HCP but LMP data are available, the registry will use first day of LMP to calculate EDD, gestational age, and DOC.

Individuals will be considered exposed during pregnancy if the exposure occurs any time from 25 days prior to the DOC to the pregnancy outcome. For the analysis of MCM, first trimester exposure will be defined as exposure from 5 times the product's half-life (i.e., 25 days for tirzepatide) prior to the DOC to 13^{6/7} gestational weeks.

